### **Anchor-based approach**

The anchor-based approach will be applied by categorizing patients according to their responses to the PGIC questions at Visit 7 (week 12).

The PGIC contains two questions (i.e. Q1 and Q1a or Q1b):

1. Compared to the start of your treatment, how would you describe your physical limitations due to heart failure today?
  - Response options: “Much better”, “Better”, “A little better”, “The same”, “A little worse”, “Worse”, or “Much worse”;
  - If a subject responds “Much better”, “Better”, or “A little better”, then he/she is asked:
    - 1a. Was this improvement in your physical limitations an important change for you?
    - Response options: “Yes”, “No”.
  - If a subject responds “Much worse”, “Worse”, or “A little worse”, then he/she is asked:
    - 1b. Was this worsening in your physical limitations an important change for you (by important we mean did it bother you)?
    - Response options: “Yes”, “No”.

Patients will be categorized according to their responses to the PGIC as follows:

- Group 1: Patients who report “A little better” to PGIC #1 as well as “Yes” to 1a;
- Group 2: Patients who report “A little worse” to PGIC #1 as well as ‘Yes’ to 1b

KCCQ PLS Mean (SD) change scores from baseline to Visit 7 (week 12) will be calculated for each group above to estimate a meaningful within-patient threshold.

KCCQ PLS mean (SD) change scores from baseline to Visit 7 (week 12) will also be calculated for the all PGIC response categories separately, to assess trends in change scores. In addition, KCCQ PLS mean (SD) change scores from baseline to Visit 7 (week 12) will be calculated by overall improvement or worsening in PGIC response categories.

### **Distribution-based approaches**

Distribution-based approaches will also be performed to supplement the anchor-based approaches. These will be based on 0.5 SD and standard error of measurement (SEM) of the KCCQ-PLS at baseline. The SEM is calculated as the standard deviation at baseline multiplied by the square root of one minus the reliability of the instrument [SD \*  $(2(1-r))^{1/2}$  ].

The reliability coefficient will be estimated by calculating correlation (Intraclass Correlation Coefficient; ICC [14, 15]) between the baseline and Week 6 KCCQ-PLS scores among stable patients. Stable patients will be defined as patients who respond ‘the same’ to the PGIC at Week 6. KCCQ-PLS mean scores for baseline and week 6, and differences between the two assessments and respective standard deviations will be reported for this stable subgroup.

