10.4 Determination of sample size

The sample size estimation for this study will be based on the analysis of the primary endpoint of KCCQ PLS at 24 weeks comparing vericiguat 15 mg versus placebo and 10 mg versus placebo, to achieve 80% power with two-sided alpha level of 0.05 to detect a treatment difference from placebo in one or both of the dose groups. A mean difference from placebo in KCCQ PLS of 5 points for both dose groups and a common SD of 21 points are assumed. Under the same assumption of treatment effect and standard deviation, the power to detect

difference for any single comparison will be 65%. The 80% power was based on an “either or” success criterion, i.e., if at least one of the primary null hypotheses is rejected. The marginal power to reject any single comparison is 65%.

The given sample size provides 97% power to detect +30 m placebo-corrected increase in the secondary endpoint 6MWT (assumed SD 80 m) for any one dose group, and 80% power to detect an increase by +22.3 m, which is below the 35 m increase associated with a 6.2 point improvement in KCCQ PLS at 24 weeks in FAIR-HF and greater than the 15 m increase at 3-months that was associated with a 2.3 point improvement in KCCQ PLS in ACTION-HF (34).

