#### 4.3.2 Anchor-based analysis and responder definitions

The main analyses to aid the interpretation and definition of a responder threshold for the KCCQ PLS change scores will be based on an anchor-based approach by categorizing patients according to their responses from baseline to Visit 7 (week 12) to the Patient Global Impression of Change (PGIC) (see Section 6.2.1). A responder definition represents the threshold for meaningful within-patient change, and it can be used to categorize patients as responders or non-responders based on the KCCQ PLS scores.

Supportive anchor-based analyses will be conducted by categorizing patients according to their change in Patient Global Impression of Severity (PGIS) (see Section 6.2.1) responses from baseline to Visit 7 (week 12) (e.g. unchanged, improved by 1 response category, deteriorated by 1 response category, etc.) and additionally, change in PGIS response between week 18 and 24 (when more subjects are expected to rate themselves in the same severity category). In addition to anchor-based approaches, supportive distribution-based approaches will also be used, i.e. 0.5 standard deviation and standard error of measurement (SEM). These methods provide an indication of the smallest score that would exceed measurement error.

Graphical displays via empirical cumulative distribution function (CDF) and probability density function (PDF), receiver operating characteristics (ROC) and non-parametric discriminant analyses will also be created to support the above estimations.

These analyses will serve to support the interpretation of study results relative to thresholds for meaningful within-patient change in addition to the established thresholds of clinically meaningful between group changes for the KCCQ PLS [11,12,13]. They will be performed on blinded data, with all treatments combined, from an interim dataset prior to study unblinding. These analyses are planned for when 100% of the patients complete Visit 7 (week 12) and their KCCQ data become available. Only patients with actual data (not imputed data) on the KCCQ PLS, PGIC, PGIS at baseline and the relevant post-baseline date (collected on the same day) will be included. The blinded analysis results will be reviewed by the PRO sub-committee which will propose an appropriate responder definition estimate for within-patient

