#### **4.3.2.1 Updates from FDA Type C meeting**

The proposed KCCQ-PLS thresholds for meaningful within-patient changes determined during the interim and blinded dataset analysis of 8.33 and 12.5 for improvement and -4.17 for worsening will be added to the pre-specified thresholds (e.g. >3, >7, >10, >15, >20) for exploratory responder analysis already included in the SAP version 1.0. Following an FDA request made during the Type C meeting held on 6th November 2019, the anchor-based analysis will be additionally run on the full trial dataset prior to unblinding to further inform interpretation of the primary endpoint of KCCQ-PLS change from baseline to week 24.

Supportive analyses, including distributional-based approaches, receiver-operating characteristic curves and non-parametric discriminant methods will not be re-evaluated on the full trial dataset prior to unblinding.

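### The SAP's worded definition of the SEM and the formula printed beside it differ by a factor of √2, and only the worded one is the SEM

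*SAP*

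**What the plan says.** SAP 4.3.2 derives responder thresholds for the KCCQ PLS mainly from the PGIC anchor and adds distribution-based checks: "These will be based on 0.5 SD and standard error of measurement (SEM) of the KCCQ-PLS at baseline". Their purpose is given in the same section: "These methods provide an indication of the smallest score that would exceed measurement error".

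The SEM is then defined in words: "The SEM is calculated as the standard deviation at baseline multiplied by the square root of one minus the reliability of the instrument". The bracket that closes this sentence prints SD × (2(1 − r))^(1/2). The reliability r is to be an intraclass correlation "between the baseline and Week 6 KCCQ-PLS scores among stable patients", stable meaning a PGIC answer of no change at week 6. The SAP gives no value for r, the baseline SD or the SEM.

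SAP 4.3.2.1 reports the outcome of the blinded interim work: "8.33 and 12.5 for improvement and -4.17 for worsening will be added to the pre-specified thresholds". It assigns these thresholds to exploratory responder analysis, and says that the distribution-based methods will not be run again on the full dataset.

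**The concern.** One sentence gives two different quantities under one name. Two programmers could each follow it faithfully and report figures 41% apart. The figure is meant to show how large a score must be to stand clear of measurement error, so a reader of the study report would set 8.33, 12.5 and −4.17 against it. Because the distribution-based work is not repeated, the interim value is the one that will stand, and no later run would reveal which formula produced it.

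**Working it through.** **Inputs**
- Worded SEM: SD × √(1 − r) (SAP, distribution-based approaches).
- Bracketed formula: SD × √(2(1 − r)) (same sentence).
- Thresholds T: 8.33, 12.5 and 4.17 in absolute value (SAP 4.3.2.1).
- SD: the baseline SD is not stated. Protocol 10.4 says "a common SD of 21 points are assumed" for the sample size. Using 21 for baseline is an assumption, and 18 to 25 is shown as a range.
- r: not stated; several values are assumed.

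The SAP prints no numerical SEM, so there is no figure of its own to reproduce.

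**Step 1: ratio.** SD√(2(1 − r)) ÷ SD√(1 − r) = √2 = 1.414, whatever the SD and r. This step needs no assumption.

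**Step 2: what each formula measures.** If one score has error variance SD²(1 − r), the difference of two scores with independent errors has error variance 2 × SD²(1 − r). The words give the error SD of one score; the bracket gives that of a difference. A simulation with SD 21 and r 0.80 gave 9.38 for one score and 13.26 for a difference, against 9.39 and 13.28 from the formulas.

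**Step 3: size in points, SD 21 assumed.**

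| r | Words | Bracket |
|---|---|---|
| 0.80 | 9.39 | 13.28 |
| 0.85 | 8.13 | 11.50 |
| 0.90 | 6.64 | 9.39 |

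**Step 4: reliability needed for T to exceed the benchmark.** By the words, r > 1 − (T/SD)². By the bracket, r > 1 − (T/SD)²/2. For T = 8.33 and SD = 21, (8.33/21)² = 0.157, so the limits are 1 − 0.157 = 0.843 and 1 − 0.079 = 0.921.

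| T | SD 18: words / bracket | SD 21: words / bracket | SD 25: words / bracket |
|---|---|---|---|
| 4.17 | 0.946 / 0.973 | 0.961 / 0.980 | 0.972 / 0.986 |
| 8.33 | 0.786 / 0.893 | 0.843 / 0.921 | 0.889 / 0.944 |
| 12.5 | 0.518 / 0.759 | 0.646 / 0.823 | 0.750 / 0.875 |

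The formulas give different answers only when r lies between the two limits in a cell.

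**Step 5: how often that happens on a coarse grid.** Take SD 20 or 24 with r 0.7, 0.8 or 0.9 (assumed).

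| SD | r | Words | Bracket | 8.33 exceeds (words / bracket) | 12.5 exceeds (words / bracket) |
|---|---|---|---|---|---|
| 20 | 0.7 | 11.0 | 15.5 | no / no | yes / no |
| 20 | 0.8 | 8.9 | 12.6 | no / no | yes / no |
| 20 | 0.9 | 6.3 | 8.9 | yes / no | yes / yes |
| 24 | 0.7 | 13.1 | 18.6 | no / no | no / no |
| 24 | 0.8 | 10.7 | 15.2 | no / no | yes / no |
| 24 | 0.9 | 7.6 | 10.7 | yes / no | yes / yes |

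The answer changes for 8.33 in 2 of 6 cells and for 12.5 in 3 of 6. A change of 4.17 is below both figures in all six.

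**The case against.** The strongest reply is that the bracket may be what was meant. The thresholds apply to within-patient change, and for a change between two scores SD × √(2(1 − r)) is the relevant error. On that view the wording is loose and the formula is right. This stands to the extent that the documents do not show which quantity was intended. It does not rescue the sentence, which names the SEM and defines it as something else.

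The second reply is that little depends on it, and this stands. SAP 4.3.2 calls the method supportive: "supportive distribution-based approaches will also be used, i.e. 0.5 standard deviation and standard error of measurement (SEM"). The 0.5 SD benchmark is the same under either formula. No section requires a threshold to exceed the SEM. A worsening threshold of −4.17 was proposed although 4.17 exceeds the worded SEM only at very high reliability (r > 0.961 at SD 21), which suggests that the SEM did not settle the proposals.

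A reader might infer more: that the benchmark actually reported is 41% too large, or that the formula decides whether 8.33 and 12.5 are acceptable. The documents support neither. They do not say which formula was run at the interim or that the thresholds were tested against the SEM, and on the assumed grid the two formulas often agree.

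A typesetting slip is possible and can be checked in the source file. It is unlikely, since the outer parentheses are needed only if the factor 2 belongs there.

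**Conclusion.** The inconsistency is certain and its size is exact: the bracket is √2 times the SEM as worded, 41% larger, and is the standard error of a difference. Reported as the SEM, the bracketed value would be mislabelled.

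The consequence is conditional and minor. The choice could change how 8.33 or 12.5 compares with measurement error, but only for reliabilities between the paired limits in Step 4. Those limits rest on an assumed SD, and r is unknown. The thresholds feed exploratory responder analyses. The MMRM in SAP 6.2.3 and the alpha control in SAP 6.2.5 do not use the SEM, and Protocol 10.5 says the blinded anchor work does not affect trial conduct. This is a correction worth making, not a threat to the trial's conclusions.

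**What to change.** 1. In SAP 4.3.2, make the words and formula agree, with SEM = SD × (1 − r)^(1/2).
2. If a benchmark for change scores is wanted, add SD × (2(1 − r))^(1/2) separately and call it the standard error of the difference.
3. State which formula was used on the interim data, with the baseline SD and r. If the bracket was used and the value was reported as the SEM, either relabel it or divide it by √2.
4. Describe all three thresholds ("8.33 and 12.5 for improvement and -4.17 for worsening") against the correctly labelled figure.

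The cost is one corrected formula and, at most, one relabelled or rescaled number with a sentence of description. No re-analysis or unblinding is needed.

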### **Empirical Cumulative Distribution Function (CDF) and Probability Density Function (PDF)**

Empirical cumulative distribution functions of the change from baseline in KCCQ-PLS scores for each PGIC anchor category will be created to show the distribution of change scores among subjects who experienced different levels of change. Examining the distribution of change scores via empirical cumulative distribution function (CDF) and probability density function (PDF) plots provides supporting evidence for the chosen responder threshold [16].

### **Receiver Operating Curves (ROC)**

ROC curves will be used to assess the ability of change in KCCQ PLS to discriminate between patients responding “a little better” with “yes” to PGIC question 1a, “better” or “much better” on the PGIC question at Visit 7 (week 12) and those with other responses. The point(s) on the curve that optimizes sensitivity and/or specificity will be considered the optimal threshold in differentiating between the two groups.

### **Non-Parametric Discriminant Analysis**

Non-parametric discriminant analysis will be conducted to explore the responder definitions [17] further. Given sufficient sample size (at least 20 patients in each of the response groups: Patients who report “A little better” to PGIC #1 as well as “Yes” to 1a; or “A little worse” to PGIC #1 as well as “Yes” to 1b; or “The same” to PGIC #1), the KCCQ PLS score density curve will be estimated for each group and the intersection points of these density curves will be considered as the discrimination points. The discrimination point between the two groups “A little better” with response “Yes” to 1a and “The same” is considered to be an estimate of the responder definition for improvement. Similarly, the estimate of the responder definition for worsening is calculated based on those who report “A little worse” with response “Yes” to 1b and “The same” to PGIC #1. In case there is not sufficient sample size in each group, patients who respond “A little better”, “Better” or “Much better” will be aggregated to the new category “Improved”. Patients who respond “A little worse”, “Worse” or “Much worse” will be combined into the new category “Worsened”. Discriminant point analysis will be performed based on these new categories in a similar way.

#### **4.3.2.1 Updates from FDA Type C meeting**

The proposed KCCQ-PLS thresholds for meaningful within-patient changes determined during the interim and blinded dataset analysis of 8.33 and 12.5 for improvement and -4.17 for worsening will be added to the pre-specified thresholds (e.g. >3, >7, >10, >15, >20) for exploratory responder analysis already included in the SAP version 1.0. Following an FDA request made during the Type C meeting held on 6th November 2019, the anchor-based analysis will be additionally run on the full trial dataset prior to unblinding to further inform interpretation of the primary endpoint of KCCQ-PLS change from baseline to week 24.

Supportive analyses, including distributional-based approaches, receiver-operating characteristic curves and non-parametric discriminant methods will not be re-evaluated on the full trial dataset prior to unblinding.

## **4.4 Data Rules**

### **4.4.1 Compliance**

The patient drug intake compliance is calculated as percent of planned tablet intake:

$$100 * \text{Number of taken tablets} / \text{Number of planned tablets}.$$

The *number of planned tablets* is calculated as: *Treatment duration (days) \* Number of planned tablets per day*. The *number of planned tablets per day* is two.

To derive *treatment duration*, the start and stop dates of tablet intake are derived from the collected study treatment exposure (dataset EX). The *number of taken tablets* is derived from the drug accountability (dataset DA).

For patients who withdraw prematurely from the study treatment, compliance will be calculated up to the time of last dose.

#### **4.4.1.1 Imputation rules for partially missing end dates for study medication**

In case of (partially) missing end dates for study medication intake the following approach will be applied to impute end of study medication intake:

- In case the subject stopped treatment due to death: impute partially missing end dates by the 'maximum study medication end date' defined as the maximal possible date (i.e. last month of the year, and last day of the month, respectively). Take the minimum of death date and, if available, imputed maximum study medication end date as the imputed study medication end date.
- In case the subject completed treatment or stopped due to reasons other than death: impute partially missing end dates by the 'minimum study medication end date' defined as the minimal possible date (i.e. first day of month and first month of year, respectively). Take the maximum of the last available study medication intake date (i.e. largest non-missing study medication start or stop date) and, if available, imputed minimum study medication end date as the imputed study medication end date.

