#### **6.3.1 Adverse events**

Adverse events (AEs) will be coded using MedDRA terminology. The version number of MedDRA used for the analyses will be stored in the clinical database. A listing will be provided linking the original investigator terms and the coded terms.

AEs are considered to be treatment-emergent if they have started or worsened after first application of study medication up to 5 calendar days after end of treatment with study medication.

An overall summary of AEs and treatment-emergent (TE) AEs will be generated by treatment group and overall.

Incidences of patients with TEAEs, drug-related and/or serious TEAEs, TEAEs causing discontinuation of study treatment will be summarized by treatment group and overall

grouped by MedDRA Primary System Organ Class (SOC) and Preferred Term (PT). In addition, the incidence of pre-treatment AEs and AEs during the follow-up (more than 5 calendar days after end of treatment with study medication) will be tabulated. Serious adverse events (SAEs), deaths, and AEs leading to discontinuation will be listed. The date, relative day (to study medication) and phase of the study (pre-treatment, during treatment, post-treatment) will be included.

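### The only end-date rule in the SAP can place a partly missing stop date too early but never too late, so it can move some on-drug adverse events out of the treatment-emergent tables

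*SAP*

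**What the plan says.** SAP 4.4.1.1 has two rules for an incomplete study-drug end date.

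- **Treatment ended by death.** The latest possible date is formed and capped: "Take the minimum of death date and, if available, imputed maximum study medication end date as the imputed study medication end date".
- **Treatment completed, or stopped for any other reason** (this includes stops caused by an adverse event). The first step is to "impute partially missing end dates by the 'minimum study medication end date' defined as the minimal possible date", that is, the first day of the month or the first month of the year. The second step sets a floor: "Take the maximum of the last available study medication intake date (i.e. largest non-missing study medication start or stop date". The later of the two dates is used.

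SAP 6.3.1 defines treatment-emergent adverse events (TEAEs) as those that "started or worsened after first application of study medication up to 5 calendar days after end of treatment with study medication". The on-treatment flag in SAP 4.1 also runs to 5 days past the end of treatment. SAP 6.3.1 sends later events to a separate table ("AEs during the follow-up (more than 5 calendar days after end of treatment with study medication) will be tabulated"). Its discontinuation incidence table is limited to TEAEs ("TEAEs causing discontinuation of study treatment will be summarized"), whereas its listings are not ("Serious adverse events (SAEs), deaths, and AEs leading to discontinuation will be listed"). The tables for symptomatic hypotension and syncope in SAP 6.3.2 also count TEAEs.

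**The concern.** TEAE incidence is the primary safety variable (Protocol 9.6), and safety is a primary objective. Protocol 3.3 says the hypotension and syncope risk at 15 mg still has to be characterised.

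For every stop other than death, the imputed end is on or before the true stop. An end date that is too early closes the treatment-emergent window too early. A patient who stops because of an event, and whose stop day was not recorded, could then have that event classed as follow-up. It would leave the TEAE table, the table of TEAEs causing discontinuation and, if it was hypotension or syncope, the special-interest tables. The error runs in one direction, towards fewer TEAEs. It arises most naturally in patients who stop early and miss the discontinuation visit, where intolerance is a plausible reason for stopping.

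**Working it through.** The plan states no figure on this point, so there is none to reproduce. The check applies the rule to dates.

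**Inputs**
- S = true stop, M = earliest date consistent with the known part, L = last recorded drug start or stop date, E = imputed end. E = max(M, L) (SAP 4.4.1.1).
- The TEAE window closes on E + 5 (SAP 6.3.1).
- Drug is dispensed at Visits 2 to 8, that is weeks 0, 2, 4, 6, 8, 12 and 18 (Protocol 7.7 and 9.1). The longest gap is 6 weeks.
- 245 patients per arm (Protocol 10.4).
- The number of incomplete dates is not given. A range of 0.5% to 5% of an arm is assumed.

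**Direction.** If the records are correct, M ≤ S and L ≤ S, so E ≤ S. An event starting on the stop day loses TEAE status when S − E > 5.

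**Worked dates, day missing**

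| True stop | Last record | Imputed end | Shift (days) | Window closes | Event on stop day |
|---|---|---|---|---|---|
| 28 Mar | 14 Feb | 1 Mar | 27 | 6 Mar | moved; 22 on-drug days fall outside |
| 28 Mar | 15 Mar | 15 Mar | 13 | 20 Mar | moved; 8 on-drug days fall outside |
| 5 Mar | 14 Feb | 1 Mar | 4 | 6 Mar | kept |

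**No later dated record** (30-day month, S uniform on days 1 to 30, E = day 1, window closes on day 6)
- Mean shift: (0 + 1 + … + 29)/30 = 14.5 days.
- Stop-day event moved: S = 7 to 30, so 24/30 = 80%.
- Event uniform over the 14 days ending on S: the share moved is (S − 6)/14 for S = 7 to 19 and 1 for S = 20 to 30. The average is (91/14 + 11)/30 = 17.5/30 = 58.3%.

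**With the SAP's floor** (400,000 simulated stops, S uniform on days 1 to 167 of treatment, random calendar start)

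| Part missing | Drug records available | Mean shift (days) | Maximum (days) | Stop-day event moved |
|---|---|---|---|---|
| Day | every dispensing visit | 8.9 | 30 | 61% |
| Day | up to week 6 only | 11.5 | 30 | 69% |
| Day | first dose only | 13.9 | 30 | 78% |
| Month and day | every dispensing visit | 14.3 | 41 | 74% |

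In the first row, about 39% of stop-day events keep TEAE status, because the shift is 5 days or less.

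**Scale per arm.** Day missing, a record at every dispensing visit, one stop-day event in each affected patient: 245 × q × 0.606, where q is the share of patients with an incomplete date.
- q = 0.5%: 0.7 events
- q = 1%: 1.5 events
- q = 2%: 3.0 events
- q = 5%: 7.4 events

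**The case against.** **The link to the TEAE window is inferred.** The rule sits under Compliance (SAP 4.4.1). Neither 6.3.1 nor 4.1 says that the imputed date sets the cut-off. A reader might infer that the SAP prescribes this use, and it does not. But it offers no other end-date rule and no exception for adverse events, so a programmer following it has only this date. The objection makes the point conditional without removing it.

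**The date is not simply the earliest possible day.** A reader who stops after the first step would infer that. The floor at the last recorded drug date limits the shift, which is why 61% rather than 80% applies when records are frequent. That drug records start at dispensing visits is itself an assumption.

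**Incomplete dates should be rare.** Last-dose timing is to be recorded at the discontinuation visit (Protocol 9.2.11) and at Visits 5, 6, 7 and 9. At Visit 9 the dose is taken on site. This stands. The exception is patients who miss those visits.

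**Moved events remain visible.** They appear in the follow-up table. Events leading to discontinuation, and all hypotension and syncope events, are listed with the study phase. This also stands, although a listing does not correct an incidence table.

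**Incidence counts patients.** Someone with another, correctly dated TEAE stays in the overall figure. The loss then shows only in rows by term and in the discontinuation and special-interest tables.

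**The death rule is not a contradiction.** A reader might see the opposite direction as one. Dosing until close to death is plausible when death ended treatment, and other stops carry no such information.

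**Conclusion.** The point holds as a conditional one. For stops other than death, the imputed end can be too early and never too late. If it is used for adverse event classification, events on drug can leave the TEAE, discontinuation and special-interest incidence tables whenever the shift exceeds 5 days. With the day missing, a stop-day event is moved in about 61% of cases if a drug record exists at each dispensing visit, rising to 80% with no later dated record. These figures assume uniform stop days and correct records.

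A reader might go on to infer that TEAE incidence is materially undercounted, or that the comparison between arms is biased. The documents do not support either. They do not say how many stop dates are incomplete, the rule is the same in all arms, and at 1% incomplete dates about 1.5 stop-day events per arm would move even if every affected patient had one. The case for change is that the error is one-directional, touches the primary safety variable and is cheap to remove.

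**What to change.** Amend SAP 4.4.1.1 as follows.

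1. For TEAE status and the on-treatment flag, use the latest possible end date, capped at death, last contact or the discontinuation visit. As long as the cap is not earlier than the true stop, no on-drug event is moved out.
2. Count as treatment-emergent any adverse event whose recorded action is 'drug withdrawn' (already collected under Protocol 9.6.1.2.4), provided it started or worsened after first dose. Without that condition, an unchanged event from before dosing could be counted.
3. Keep the present rule for exposure, duration and compliance.
4. Report the number of imputed end dates by arm.

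The cost is a few sentences and some programming. A few patients will carry two end dates, and a few post-treatment events may be counted as TEAEs, which is the safer error for a safety variable. No new data are needed.
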